4.1. Treatment Misallocation

All analyses will be performed on an “as-treated” basis and will not include data from participants who are randomized but not treated.

If a participant takes a treatment that is not consistent with the treatment they are randomized to, for example takes a treatment out of sequence or takes the same treatment twice, then they will be reported under the treatment that they actually receive for all safety, PK and pharmacodynamic analyses, where applicable.

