4.1.2. Part 2: Participants with Atopic Dermatitis

Part 2 is a randomized, participant- and investigator-blind, sponsor-open, placebo-controlled investigation of the safety, tolerability, PK, and pharmacodynamics (including effects on clinical signs and symptoms) of PF-07242813 in adult participants with moderate to severe atopic dermatitis (AD).

In Part 2, Cohort 9 will randomize (2:1, PF-07242813) 24 participants at the MTD defined in Part 1 (or maximum dose studied in Part 1 if MTD is not achieved) for the assessment of the safety, tolerability, PK, and clinical effects of PF-07242813 in AD and **CCI** [REDACTED]. The number of participants enrolled in Cohort 9 will provide a sample size sufficient for statistical evaluation of the primary efficacy endpoint (placebo-corrected percent change from baseline in continuous EASI).

Cohort 9 will be initiated following completion of all single dose cohorts evaluated in Part 1 and review of cumulative safety and PK data from Part 1. Participants in Cohort 9 will receive the study intervention on Day 1 at the MTD identified in Part 1, or the highest dose studied in Part 1 if MTD is not achieved. The dose will be administered at the clinical site, and participants will return for outpatient visits per the [Schedule of Activities \(Table 3\)](#), up to Week 16.

An optional cohort (Cohort 16) of up to 24 moderate to severe AD participants may be enrolled as needed to evaluate further IV or SC dosing, based on cumulative safety and PK data from Part 1 and Cohort 9 in Part 2.

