9.4.1. Efficacy Analyses (Part 2 Only)

Endpoint	Statistical Analysis Methods
Secondary (percent change from baseline)	A landmark analysis using analysis of covariance of percent change from baseline in EASI, adjusting for the baseline EASI score, to estimate the effect of the initially randomized treatment in the absence of prohibited medication. The analysis will use the mITT analysis set. Missing data due to any cause including censoring due to initiation of prohibited medication will be imputed using the corresponding vehicle arm, missing data in a vehicle arm will be imputed using data from the vehicle arm assuming data are missing at random (MAR). The analysis will combine the results from the multiple imputations using Rubin's rule's as implemented in SAS PROC MIANALYZE.
CCI	[REDACTED]
[REDACTED]	[REDACTED]

[REDACTED]

[REDACTED]

[REDACTED]

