2.2. Study Design

This is a first-in-human (FIH) study of PF-07242813 that will be conducted in 2 parts: Part 1 will be conducted in healthy adult participants and Part 2 will be conducted in participants with moderate to severe AD (see [Figure 1](#)).

Part 1 is within-cohort randomized, participant- and investigator-blind, sponsor-open, placebo-controlled investigation of the safety, tolerability, PK, and immunogenicity following single and multiple ascending doses of PF-07242813 in healthy participants. Part 1 will also include a cohort of Japanese healthy adult participants (Cohort 15) to provide safety, tolerability, and PK data in Japanese population to enable the inclusion of Japanese participants in future clinical trials.

Part 2 is a randomized, participant- and investigator-blind, sponsor-open, placebo-controlled investigation of the safety, tolerability, PK, and pharmacodynamics (including clinical effects) of PF-07242813 in participants with moderate to severe atopic dermatitis (AD). The first cohort in Part 2 (Cohort 9) will enroll 24 participants for the assessment of the clinical effects of PF-07242813 in AD and exploratory evaluations of pharmacodynamic activity. The number of participants enrolled in Cohort 9 will provide the total sample size (N=24) for statistical evaluation of the primary efficacy endpoint (placebo-corrected percent change from baseline in continuous EASI). Participants in Cohort 9 will receive the MTD defined in Part 1.

Figure 1. C4461001 Study Design

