4. ANALYSIS SETS (POPULATIONS FOR ANALYSIS)

Data for all participants will be assessed to determine if participants meet the criteria for inclusion in each analysis population prior to unblinding and releasing the database and classifications will be documented per standard operating procedures.

Population	Description
Modified Intention to Treat (mITT)	All participants randomly assigned to study intervention and who apply at least 1 dose of study intervention.
PK concentration set	All enrolled participants who applied at least one dose of PF-07242813 and in whom at least once concentration value is reported.
PK parameters	The PK parameter analysis population will be defined as all randomized participants who received at least 1 dose of study intervention and who have at least 1 of the PK parameters of interest calculated.
Safety Analysis Set	All participants randomly assigned to study intervention and who receive at least 1 dose of study intervention. Participants will be analyzed according to the product they actually received.

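### SAP 4.1 puts every analysis on an as-treated basis with no efficacy exception, which conflicts with the protocol's Week 6 EASI analysis by randomized treatment

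*SAP*

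**What the plan says.** SAP 4.1 (Treatment Misallocation) contains two rules. The first is general: "All analyses will be performed on an “as-treated” basis", with participants who were randomized but never treated left out. The second covers anyone whose treatment does not match the randomization. They are "reported under the treatment that they actually receive for all safety, PK and pharmacodynamic analyses", followed by a where-applicable qualifier. Efficacy is neither named nor exempted.

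Protocol 9.4.1 describes the Week 6 EASI ANCOVA, on the mITT set, as intended "to estimate the effect of the initially randomized treatment in the absence of prohibited medication".

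SAP 4 defines mITT as "All participants randomly assigned to study intervention and who apply at least 1 dose of study intervention". That settles who is in the set, not which arm they are counted in. The Safety set in the same table does state an assignment rule: "Participants will be analyzed according to the product they actually received".

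SAP 6.2.1.1 runs the EASI ANCOVA on mITT with treatment arm as a factor and does not say whether that means the randomized or the actual arm. SAP 5.1.2 makes rejection of this null hypothesis the condition for a positive study.

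**The concern.** Section 4.1 is the only visible SAP text that gives an assignment rule reaching the EASI analysis, and it says as-treated. The protocol points the other way. A programmer following the SAP literally would move a misdosed participant to the arm of the product received. One following the protocol would not.

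Analysis by randomized arm keeps the comparison protected whatever caused the error. Under the null hypothesis of no drug effect, an as-treated comparison keeps that protection only if the error is unrelated to prognosis. The study is also sponsor-open, and protocol 9.5 allows unblinded data reviews during conduct. If an error occurred, the choice between two conflicting rules could be made by people who can see allocation and outcome, which is the situation pre-specification is meant to prevent. Protocol 8.3.10 recognises that study drug may be given to the wrong participant.

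**Working it through.** **Texts side by side**

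| Place | Assignment rule for the EASI test |
|---|---|
| SAP 4.1, first sentence | As-treated, all analyses |
| SAP 4.1, second rule | Actual treatment for safety, PK and pharmacodynamics, where applicable; efficacy not named |
| Protocol 9.4.1 | Initially randomized treatment, mITT |
| SAP 4, mITT | None stated |
| SAP 6.2.1.1 | Treatment arm, not specified further |
| SAP Appendix 6 sample code | Models a variable called dose, not tied to the randomized arm |
| SAP 1, version history | No change to the assignment rule declared |

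The SAP is allowed to modify the protocol (protocol 9, SAP 2), but nothing in the version history presents this as a deliberate change.

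**Inputs for scale** (SAP 5.1.2, protocol 9.2.2): 24 participants at 2:1, so 16 active and 8 placebo; difference 50; SD 46; one-sided alpha 0.05. The documents give no dosing-error rate, so one error (or one swap) is an assumption.

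**The plan's own figure.** The standard error of the difference is 46 × √(1/8 + 1/16) = 46 × 0.433 ≈ 19.9. Power is 80.7% by the normal approximation and 78.4% by the noncentral t with 22 df. Both agree with the stated figure of approximately 80%.

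**Expected difference by randomized arm**
- One placebo participant given active drug: 50 × (1 − 1/8) = 43.75, a loss of 6.25, or 6.25/19.9 ≈ 0.3 standard errors.
- One active participant given placebo: 50 × (1 − 1/16) = 46.875, a loss of about 3.1, or about 0.16 standard errors.
- One swap (both of the above): 50 × (1 − 1/8 − 1/16) = 40.625.

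**Expected difference as-treated.** It stays at 50 in each case, provided the error is unrelated to prognosis. The arms become 17:7, 15:9 and 16:8.

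| Assumed error | By randomized arm: difference, power | As-treated: difference, power |
|---|---|---|
| One placebo given active | 43.75, 68.6% | 50, 75.8% |
| One active given placebo | 46.9, 73.7% | 50, 80.3% |
| One swap | 40.6, 63.0% | 50, 78.4% |

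Powers are two-sample t values with SD held at 46. They ignore baseline adjustment and the extra spread from a mixed arm, so they indicate scale only.

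**The case against.** The strongest reply is that the documents nearly answer the question already. Protocol 9.4.1 is specific. The SAP assigns EASI to mITT, and only the Safety set is tied to the product received, so the contrast favours reading mITT as by randomized arm. The first sentence of SAP 4.1 goes on to exclude untreated participants, which matches mITT. Its examples (treatment out of sequence, the same treatment twice) do not fit a single-dose parallel cohort, so the wording looks generic. All of this stands. It shows that the section was probably not a deliberate choice for EASI, but it does not remove an unqualified sentence that says the opposite of the protocol.

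A reader might infer that the second rule in SAP 4.1 captures EASI as well, because SAP 2.2 speaks of "pharmacodynamics (including clinical effects) of PF-07242813" and protocol 4.1.2 is similar. The documents do not support that. These are study-design descriptions, and SAP 2.2 itself goes on to list clinical effects and pharmacodynamic activity separately. EASI is handled as efficacy in protocol 9.4.1, SAP 5.3.2 and SAP Appendix 2, and the rule carries its where-applicable qualifier. The pharmacodynamic sections of the protocol are largely redacted and cannot be checked further. The conflict rests on the first sentence of SAP 4.1 alone.

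The event is also unlikely. A second staff member verifies dispensing (protocol 6.2.1), and someone other than the person dosing confirms dose and identity (protocol 6.4). That limits the importance of the point but not its correctness.

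**Conclusion.** The conflict is real. SAP 4.1, read literally, would analyse the decisive EASI test by treatment received, while protocol 9.4.1 targets the randomized treatment, and no visible SAP text reconciles them.

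It is not settled that a misdosed participant would in fact change arms. Two rules conflict, and either could be followed. Nor does reassignment by treatment received move the placebo mean by about 6 points in either direction. The 6.25-point figure is the expected dilution under the randomized-arm rule when a placebo participant receives active drug. Under as-treated, someone moved into placebo actually received placebo, so the expected shift in that mean is zero.

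The size is modest and conditional. Nothing changes unless a dosing error occurs, and no stated sample size, power or alpha is affected. With one error, the expected difference depends on the rule by about 3 to 6 points against a standard error of 19.9, and power by roughly 7 percentage points; a swap moves power by about 15. These figures assume a true difference of 50 and an error unrelated to prognosis. In each case as-treated gives the larger expected effect, which is a further reason to fix the rule in advance.

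**What to change.** Limit SAP 4.1 to safety, PK and biomarker analyses. Add to the mITT definition in SAP 4, and to 6.2.1.1, that EASI and the other efficacy endpoints are analysed by randomized arm regardless of product received. An as-treated analysis of EASI can be added as a sensitivity analysis if wanted. Check that the treatment variable in the EASI program is the randomized assignment.

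The cost is two or three SAP sentences, with no change to sample size, conduct or data collection. The downside is a slightly diluted estimate, and some loss of power, if a misdosing occurs.

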4.2. Protocol Deviations

Participants who experience events that may affect their PK profile may be excluded from the PK analysis. At the discretion of the pharmacokineticist, a concentration value may also be excluded if the deviation in sampling time is of sufficient concern or if the concentration is anomalous for any other reason.

A full list of protocol deviations will be compiled and reviewed to identify major and minor deviations prior to database closure.

5. GENERAL METHODOLOGY AND CONVENTIONS

The primary analysis of atopic dermatitis cohort will be performed when all randomized subjects have either completed their 6-week study participation period or withdrawn early or should the study be stopped prematurely due to any reason, and the database is released.

5.1. Hypotheses and Decision Rules

5.1.1. Part 1 - Healthy Adult Participants

5.1.1.1. Statistical Hypotheses

No classical hypothesis testing will be performed.

5.1.1.2. Statistical Decision Rules

Not applicable.

5.1.2. Part 2 - Atopic Dermatitis Participants

Statistical inference will be made on the secondary endpoint: (percentage change from baseline in EASI score at Week 6). The null hypothesis is that there is no difference between the treatment group and the placebo group. The alternative hypothesis is that the treatment group (PF-07242813 arm) is superior to the placebo group at Week 6. The study will be considered positive, if this null hypothesis is rejected.

The sample size calculation is based on the secondary endpoint (percent change from baseline in EASI score at Week 6). A total of 24 randomized participants with a randomization ratio of 2:1 into the treatment and placebo group will provide approximately 80% power to detect a difference of 50 in percent change from baseline with a common standard deviation 46% between PF-07242813 and the placebo arm with 1-sided alpha=0.05.

Cohort 9 will enroll 24 participants with moderate to severe AD at the MTD.

5.2. General Methods

5.2.1. Statistical Method: Part 1 - Healthy Participants Single and Multiple Ascending Dose

Given the exploratory nature, descriptive statistics and graphic visualization will be provided for these segments. No formal statistical hypothesis testing is planned.

5.2.2. Analyses for Binary Endpoints: Part 2 – Atopic Dermatitis Participants

Landmark (cross-sectional) analyses of key binary endpoints will calculate and test for risk differences using the method of Chan and Zhang (1999).² Risk differences, 90% confidence interval and 1-sided p-value will be presented.

For all binary endpoints, a summary based on the mITT Observed Efficacy Set of the number of subjects in each category based on observed cases in each treatment arm at each time point will be produced and the response rate will also be plotted against time, by treatment group.

Exploratory categorical analyses that include or assess the effects of covariates may be done on an exploratory basis. Exploratory longitudinal analyses may also be performed

5.2.3. Analyses for Continuous Endpoints: Part 2 - Atopic Dermatitis Participants

Landmark (cross-sectional) analysis of key continuous endpoints will use analysis of covariance (ANCOVA). The ANCOVA model will include terms for treatment arm and baseline score of the dependent variable. Least-squares means at the mean overall baseline score will be presented along with 90% confidence intervals.

Mixed model repeated measures (MMRM) models will be used. The fixed effects of treatment, visit (Weeks 1, 2, 3, 4, and 6), and treatment-by-visit interaction will be included. Visit will be modeled as a categorical covariate. Unstructured covariance matrix will be assumed for the model errors. Compound symmetry covariance matrix will be used if the model with unstructured covariance doesn't converge.

When modeling the percentage change from baseline values, the variable for visit will start with the first post-baseline visit, and the actual baseline value will be included as a covariate. At each visit, estimates of least square mean (LSM) values and the LSM differences between the PF-07242813 and the placebo arm will be derived from the model. The corresponding p-values and 90% confidence intervals will also be derived from the model.

Unless stated otherwise, descriptive summary statistics for all continuous variables will be presented on mITT observed data by treatment group and will include the following: n, mean, median, standard deviation, minimum and maximum.

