1. VERSION HISTORY

Table 1. Summary of Changes

Version/ Date	Associated Protocol Amendment	Rationale	Specific Changes
1 30 NOV 2020	Original 30 Sep 2020	N/A	N/A
2 01 Sep 2022	Protocol Amendment 2 10 Jul 2021	To be consistent with Protocol Amendmen t 2	
 Section 6.2.2. Added details of NRS endpoint analysis. Section 6.2.5. Removed the summary of dosing compliance according study team agreement. Section 6.3. Added details of immune-based AEs. Section 6.3.4. Modified the language of vital signs analysis. Appendix 3. Visit window was updated and added window definition for NRS endpoints. Appendix 6. Modified the SAS code for Estimand 1 to be consistent with Section 6.2.

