3.2.3. Other Endpoint(s): Tertiary/Exploratory

- *Serum PF-07242813 concentrations after administration will be determined by a validated assay.*
- *Proportion of participants achieving IGA score of clear (0) or almost clear (1) (on a 5 point scale) and a reduction from baseline of ≥ 2 points at Week 6 and other time points specified in the SoA.*
- *Percent change from baseline in EASI total score at time points in the SoA.*

- *Proportion of participants with moderate to severe AD achieving EASI-50/EASI-75/ EASI-90/EASI-100 (respectively 50%, 75%, 90%, and 100% improvement from baseline), at Week 6 and other time points specified in SoA.*
- *Incidence of development of antidrug antibodies (ADAs) and if appropriate, neutralizing antibodies (NAbs).*
- *Change from baseline in select anterior pituitary hormones levels and hormones regulated by them in blood that may include (but may not be limited to): HGH, IGF-1, TSH, T4 and Cortisol.*
- *Change from baseline in blood cytokine levels that may include, but not be limited to, TNF α , IL-6 and IFN γ if performed in concordance with clinical symptoms of cytokine release.*
- *Change from baseline in circulating biomarkers which may include Total IgE, TARC (CCL17), IL-31, IL-17A, eosinophils and lymphocyte subsets.*
- *Change from baseline in gene expression and/or histological endpoints may be measured from skin biopsies.*
- *Change from baseline in Patient-Oriented Eczema Measure (POEM) at Week 6 and at all other time points specified in the SoA.*
- *Change from baseline in Dermatology Life Quality Index (DLQI) at Week 6 and at all other time points specified in the SoA.*
- *Change from baseline in pruritus severity and frequency in Pruritus Numeric Rating Scale) at Week 6 and at all other time points specified in the SoA.*

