Appendix 2. Summary of Efficacy Analyses

Efficacy Endpoint	Analysis Type	Population	Data Inclusion and Rules for Handling Intercurrent Events and Missing Data	Analysis Model/Method
Week 6 PCFBL in EASI	Primary Analysis	mITT	MI	ANCOVA
All Visits IGA Response	Secondary Analysis	mITT	NRI	Chan and Zhang (1999) ²
All Visits CFBL PP-NRS Response	Secondary Analysis	mITT	OD	MMRM
All Visits EASI – 75 Response	Secondary Analysis	mITT	NRI	Chan and Zhang (1999) ²
CCI				
	Main analysis	mITT	All data collected will be included regardless of intercurrent events. Missing data will be imputed.	ANCOVA
	CCI			

PCFBL= Percent change from baseline; CFBL= Change from baseline; ANCOVA = Analysis of Covariance; OD = Observed data.

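### The visible SAP text puts baseline in the repeated-measures model only for percentage change, while the one visible endpoint assigned to that model, exploratory itch, is a plain change score

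*SAP*

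**What the plan says.** SAP 5.2.3 describes two methods for continuous Part 2 endpoints.

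- **Landmark ANCOVA.** "The ANCOVA model will include terms for treatment arm and baseline score of the dependent variable".
- **MMRM.** "The fixed effects of treatment, visit (Weeks 1, 2, 3, 4, and 6), and treatment-by-visit interaction will be included". A following paragraph opens "When modeling the percentage change from baseline values, the variable for visit will start with the first post-baseline visit" and goes on to say that "the actual baseline value will be included as a covariate". That is the only place in the visible text where baseline enters the MMRM.

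In SAP Appendix 2, the only visible row with MMRM as its method is "All Visits CFBL PP-NRS Response", analysed on observed data in the mITT set. The footnote keeps the two scales apart: "PCFBL= Percent change from baseline; CFBL= Change from baseline". SAP 3.2.3 also defines the itch endpoint on the change scale, under tertiary/exploratory endpoints: "Change from baseline in pruritus severity and frequency in Pruritus Numeric Rating Scale".

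Three places that could settle the matter cannot be read in the public copy. They are SAP 6.2.2 (the version history records "Added details of NRS endpoint analysis" there), Appendix 7 on the repeated-measures model, and some rows of Appendix 2.

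**The concern.** The condition attached to the baseline covariate is percentage change, and the visible endpoint to which the model applies is not on that scale. An analyst working from 5.2.3 alone could fit treatment, visit and their interaction to itch change scores, without baseline, and be following the text.

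That would sit oddly with the rest of the SAP. The ANCOVA in the same section adjusts for the baseline score, and the illustrative code in Appendix 6 regresses plain EASI change on baseline and dose.

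Precision is what would be at stake. With 16 active and 8 placebo participants, chance baseline differences can be sizeable, and an unadjusted change score carries part of any such difference into the estimated effect. In a sponsor-open study it is also useful to have the covariate fixed in advance.

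**Working it through.** **The plan's own figure.** No power, SD or correlation is given for itch. The only stated figure is about 80% power for Week 6 percent change in EASI: difference 50, SD 46, 24 participants at 2:1, 1-sided alpha 0.05 (Protocol 9.2.2, SAP 5.1.2).

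- SE = 46 × √(1/8 + 1/16) = 46 × 0.433 = 19.9.
- 50/19.9 = 2.51, and 2.51 − 1.645 = 0.865, which gives 80.7% power (normal approximation).
- A noncentral t with 22 df gives 78.4%.

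The figure reproduces. It confirms the 16 versus 8 split but says nothing about itch.

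**Cost of omitting baseline, equal SDs (assumed).** Take SD s at both times and correlation ρ, comparing two arms at one visit.

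- Variance of a change score: 2(1−ρ)s².
- Variance after adjusting for baseline: (1−ρ²)s².
- Ratio, unadjusted to adjusted: 2/(1+ρ).

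| ρ (assumed) | Variance ratio | Adjusted SE ÷ unadjusted SE | Adjusted power where the unadjusted analysis has 80% |
|---|---|---|---|
| 0.3 | 1.54 | 0.81 | about 92% |
| 0.5 | 1.33 | 0.87 | about 89% |
| 0.7 | 1.18 | 0.92 | about 85% |

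Powers use the normal approximation.

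**Unequal SDs (assumed).** Baseline SD 2, follow-up SD 2.5, ρ = 0.5.

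- Change: 4 + 6.25 − 2 × 0.5 × 2 × 2.5 = 5.25, so SE = 0.433 × √5.25 = 0.99 points.
- Adjusted: 6.25 × (1 − 0.25) = 4.69, so SE = 0.433 × √4.69 = 0.94 points.
- Ratio: 5.25/4.69 = 1.12. The unadjusted analysis would need about 24 × 1.12 ≈ 27 participants to match.

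**Chance imbalance.** One standard error of the baseline difference is 0.433 SD with 16 versus 8.

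- Equal SDs: the shift in the unadjusted estimate is (1−ρ) × 0.433, or 0.30, 0.22 and 0.13 SD for ρ = 0.3, 0.5 and 0.7. That is 0.59, 0.50 and 0.39 of that estimate's own SE.
- Unequal SDs as above: the slope is 0.5 × 2.5/2 = 0.625 and the imbalance is 2 × 0.433 = 0.87 points, so the shift is 0.375 × 0.87 ≈ 0.32 points.

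This is not a second harm. Since (1−ρ²) + (1−ρ)² = 2(1−ρ), the carried-over imbalance is exactly the extra variance in the table.

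**Small-sample allowance.** Estimating the baseline slope multiplies the adjusted variance by about 1 + 1/(24−4) = 1.05 on average. Dividing by 1.05, the range 1.54 to 1.18 becomes about 1.47 to 1.12, and 1.12 becomes about 1.07.

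**The case against.** A reader might infer that the itch analysis is unadjusted for baseline, or that itch is the model's only use. The documents do not support either statement. Section 5.2.3 is general methods. The endpoint-specific itch text (6.2.2) and the model appendix (Appendix 7) are redacted, and redacted text cannot be counted as absent. Both may include baseline. Other MMRM rows may also sit in the redacted part of Appendix 2.

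The restrictive reading of 5.2.3 can itself be challenged. The section never says that baseline is left out for change scores. The same sentence starts the visit variable after baseline. If that applied only to percentage change, nothing in it would keep the baseline visit, where change is zero for everyone, out of a change-score model. Loose wording is a fair explanation, and the ANCOVA rule fits it.

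A reader might also infer bias. Under randomisation an unadjusted comparison of change scores is unbiased on average.

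The stakes are limited too. Appendix 2 labels the itch row a secondary analysis, but SAP 3.2.3 lists itch as exploratory. The trial's success criterion in SAP 5.1.2 rests on Week 6 EASI, which is adjusted for baseline (SAP 6.2.1.1). The sizes above rest entirely on assumed SDs and correlations.

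All of this stands and keeps the grade low. None of it makes the visible sentence cover the endpoint that the visible table assigns to the model.

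**Conclusion.** The point holds as a gap in the visible wording: 5.2.3 ties the baseline covariate to percentage change, the visible MMRM endpoint is plain change in itch, and no visible rule adjusts that comparison. Whether the full SAP adjusts it cannot be determined from the public copy.

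If baseline were omitted, the loss would be precision. The variance of the treatment difference would be about 1.18 to 1.54 times the adjusted one for ρ from 0.7 to 0.3 with equal SDs, and about 1.12 times in the unequal-SD example, before a small-sample allowance of about 5%. No itch SD or ρ appears in the documents, so these are illustrations over a range. The EASI conclusion is not affected. Low severity; a free improvement.

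**What to change.** In SAP 5.2.3, widen the opening condition of the percentage-change sentence so that it covers change as well as percentage change from baseline. Leave the rest of the sentence, including the baseline covariate, as it is. Then check that Section 6.2.2 and Appendix 7 state the same model. If they already include baseline, the edit only brings the general text into line with them; if they follow 5.2.3 as it reads now, the edit closes the gap.

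The cost is a few words and one model term. The Day 1 pruritus NRS is already collected before dosing (Protocol Table 3). A baseline-by-visit term is optional: with 24 participants and an unstructured covariance it is a matter of preference, and the SAP's own percentage-change model does not state one.
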